- **Assessment for recurrence of inflammation**
- Confocal or specular microscopy if recurrent
- **Anterior chamber paracentesis #3 if recurrent inflammation (participant exits study if recurrent inflammation)**

**Exam 5
(7 months after
randomization)**

- Clinical eye examination (in following order, VA, slit lamp examination of anterior segment, IOP)
- **Assessment for recurrence of inflammation**
- Confocal or specular microscopy if recurrent
- **Anterior chamber paracentesis #3 if recurrent inflammation (participant exits study if recurrent inflammation)**

**Exam 6
(9 months after
randomization)**

- Clinical eye examination (in following order, VA, slit lamp examination of anterior segment, IOP)
- **Assessment for recurrence of inflammation**
- Confocal or specular microscopy if recurrent
- **Anterior chamber paracentesis #3 if recurrent inflammation (participant exits study if recurrent inflammation)**

**Exam 7
(11 months after
randomization)**

- Clinical eye examination (in following order, VA, slit lamp examination of anterior segment, IOP)
- **Assessment for recurrence of inflammation**
- **Anterior chamber paracentesis #3 if recurrent inflammation (participant exits study if recurrent inflammation)**

Exam 8
(12 months after
randomization,
Final Visit)

- Clinical eye examination (in the following order, VA, slit lamp examination of anterior segment, IOP)
- **Assessment for recurrence of inflammation**
- **Anterior chamber paracentesis #3 if recurrent inflammation (participant exits study if recurrent inflammation)**

Note that participants will be advised to contact their local site clinical coordinator or study ophthalmologist if they are having symptoms of recurrent inflammation. Recurrent inflammation is typically symptomatic (characterized by ocular redness, decreased vision, light sensitivity, and pain). Thus, participants will be evaluated for symptoms of recurrent inflammation, which may occur between study visits, during which they would have clinical eye examination, anterior chamber paracentesis #3 (if there is recurrent (active) inflammation).

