1.2 Schedule of Activities (SOA)

Tasks/Forms	Trial I Visits				Trial II Visits		
	Exam #0	Enroll/ Randomize Exam #1	Exam #2	Exam #3	Enroll/ Re-Randomize Exam #1	Exam #2-7	Exam #8
Eligibility/ Screening Form		X			X		
Consent/HIPAA		X			X		
Baseline History Form		X					
Clinical Eye Exam Form		X	X	X	X	X	X
REDCap patient		X			X		
Treatment initiation		X			X		
Laboratory orders (CBC, Cr, pregnancy	X		X	X		X	X
SAE/side effect evaluation			X	X		X	X
Calendar/ medication log***			X	X		X	X
Patient Dropout		(x)	(x)	(x)		(x)	(x)
Protocol Deviation Form	(x)	(x)	(x)	(x)	(x)	(x)	(x)
Adverse Event Narrative/Log	(x)	(x)	(x)	(x)	(x)	(x)	(x)
AC paracentesis	X		X			(x)	(x)

Confocal microscopy				X			X
(x)-if applicable							

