2.3 Risk/Benefit Assessment

2.3.1 KNOWN POTENTIAL RISKS

The Medication risks:

Patients randomized to receive oral valganciclovir will be at risk of developing complications due to systemic toxicity. Although this drug is widely prescribed to treat CMV anterior uveitis in the United States, there are known adverse effects. Common ones include fever, headache, insomnia, diarrhea, nausea, vomiting, and abdominal pain. Rare side effects include hematologic abnormalities, acute renal failure, infertility, teratogenesis, and carcinogenesis. Patients randomized to receive topical ganciclovir eye drops will be subjected to the risks of topical toxicity. These include corneal epitheliopathy and conjunctivitis, both of which are almost always reversible upon discontinuation of the topical medication.

Minimizing medication risks:

Due to the potential complications associated with oral valganciclovir, patients will obtain pre-study labs, as well as monitoring labs throughout the study. The pre-study labs are to ascertain whether an individual is at greater risk of developing complications such as bone marrow suppression or acute renal failure. Patients identified as being high risk will be excluded from the study, as specified in our protocol. Patients enrolled in the study will receive regular laboratory tests in order to monitor CBC and renal function. Those that develop blood or renal abnormalities as specified in the protocol will be removed from the study. For patients that are randomized to receive topical antiviral therapy, the regular schedule of follow-up with clinical exam by a study ophthalmologist will provide ample opportunity to detect topical toxicity and discontinue medications as described in our protocol.

Procedural risks:

Although extremely rare, risks associated with anterior chamber paracentesis include endophthalmitis and traumatic cataract, both of which can lead to vision loss. In rare cases, endophthalmitis warrants need for eye removal.

Minimizing procedural risk:

All study ophthalmologists are trained to safely utilize anterior chamber paracentesis techniques to access fluid in the anterior chamber. Sterilization drops will be used in order to minimize the risks of intra-ocular infection.

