- The study coordinator will check-in with the patient and complete the following in any order:
 - Review of patient medication diaries
 - Review of adverse events since last visit*
 - Dispense new medication bottle (*if applicable*)

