7.2.1 NON-SERIOUS ADVERSE EVENTS

Non-serious adverse events may include any unfavorable medical occurrences in patients who have ever received study medication, regardless of any causal relationship with treatment. Examples may include:

1. Increased intraocular pressure (>24 mm Hg)
2. Abnormal lab findings (rise in creatinine to ≥ 1.5 to < 2 mg/dL, reduction of white blood cell count to below 2.5)
3. Concurrent accident or illness
4. Increase in the frequency and severity of symptoms of a pre-existing condition
5. Side effects intolerable to patient (gastrointestinal upset, nausea, vomiting, fatigue)
6. Signs of corneal or conjunctival toxicity (epitheliopathy, conjunctivitis)

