7.2.5 ADVERSE EVENT REPORTING

Non-serious and serious adverse events will be noted at each study visit by the study coordinator while meeting with the patient at the beginning of each study visit. If there are any reported symptoms (not only severe symptoms), the study physician will review them with the patient while remaining masked to determine if any action is needed.

In case of a Serious Adverse Event (SAE), the Investigator needs to write a summary of the SAE and submit to the Medical Monitor ([name]; [contact]), and Principal Investigator ([name]; [contact]) within 24 hours of the SAE. Information recorded in this message will include the nature of the event, date of onset, date of resolution, date of notification to Medical Monitor, and action taken. The Medical Monitor will review and decide if the serious adverse event was related to the study drug and collect additional information if needed.

The Medical Monitor will determine two things:

- 1) Whether this is a true adverse event and
- 2) Whether this is likely related to the study drug.

If the investigator thinks the SAE is related to the study drug, he/she can stop the study medication anytime (including prior to investigation by the medical monitor).

Any significant study drug-related adverse events will be reported by the coordinating center to the FDA and CHR office as appropriate. The principal statistician will inform the DSMC of serious adverse events by arm every month.

Any complications will be reported within 24 hours to the Principal Investigator ([name], [contact]).

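### No scheduled safety contact or adverse-event window follows paracentesis #3 in Trial II, so a delayed harm of the tap depends on spontaneous reporting

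*Protocol*

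**What the plan says.** **The tap and the exit.** The schema in Protocol 1.1 has the same line at every Trial II follow-up visit, Exams 2 to 8: "Anterior chamber paracentesis #3 if recurrent inflammation (participant exits study if recurrent inflammation". Symptomatic flares are also evaluated off schedule: "which may occur between study visits, during which they would have clinical eye examination, anterior chamber paracentesis #3". The Schedule of Activities (1.2) has no column for these extra visits.

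**The named harms.** Protocol 2.3.1 says "risks associated with anterior chamber paracentesis include endophthalmitis and traumatic cataract, both of which can lead to vision loss". The same sentence describes these risks as extremely rare. The mitigation given is operator training and sterilizing drops. For topical drug toxicity, by contrast, 2.3.1 relies on the regular follow-up examinations.

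**When adverse events are collected.** Section 7.2.5 has the coordinator note them "while meeting with the patient at the beginning of each study visit". Section 4.1.1, headed for Exams 2 and 3, describes the check-in task as "Review of adverse events since last visit". The schedule row "SAE/side effect evaluation" is marked in Trial II for Exams 2-7 and Exam 8 only.

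**Duties not tied to a visit.** Section 7.2.5 adds "Any complications will be reported within 24 hours to the Principal Investigator". Section 7.2.1 defines non-serious events as "any unfavorable medical occurrences in patients who have ever received study medication, regardless of any causal relationship with treatment". Neither gives a closing date.

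**After a serious event.** Section 7.2.4 asks that a participant with an SAE keep attending scheduled visits where possible.

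**The concern.** The protocol identifies the tap as a procedure that can cost vision, yet in Trial II it places the tap at the point where active follow-up ends. A reporting duty begins only when someone at the site learns of an event. After exit, that depends on the participant returning or the site volunteering the information.

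Two things are at stake. First, Trial I and Trial II would report complications of the same procedure with different ascertainment, and a low count in Trial II could be read as reassurance when part of it reflects less looking. Second, the taps fall by arm in proportion to recurrence, which is the Trial II primary outcome. The proportions with adverse events and SAEs are to be compared by arm with Fisher's exact test (Protocol 8.3.1, SAP 3.5). If recurrence differs as the trial hypothesizes, the unobserved post-tap periods are concentrated in the arms with more recurrences.

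**Working it through.** **Step 1. Sequence of events at the two taps.**

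| | Trial I, paracentesis #2 | Trial II, paracentesis #3 |
|---|---|---|
| When | Exam 2, day 7 | Visit at which recurrence is found |
| Adverse-event review at that visit | At its start | At its start |
| Next scheduled safety evaluation | Exam 3, day 21 (21 − 7 = 14 days later) | None; participant has exited |

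A tap at Exam 8 has no later visit in any case. At Exams 2 to 7 it is the exit rule that removes the later visits. A search of both documents finds no visit, call or adverse-event window after exit.

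**Step 2. The plan's own recurrence count.** SAP Table 1 has 18 + 38 = 56 completers in the two active Trial II arms. At the SAP's 60% recurrence, 56 × 0.60 = 33.6, which reproduces the stated 34.

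**Step 3. Taps at exit, by arm.** Inputs from SAP 3.3: 28 evaluable per arm (105 × 0.80 = 84 in all), 25% recurrence on placebo, 65% on oral valganciclovir.
- Placebo: 28 × 0.25 = 7.0
- Oral: 28 × 0.65 = 18.2
- Ratio: 18.2 / 7.0 = 2.6

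**Step 4. Total taps at exit.** Neither document gives an arm-specific recurrence risk for topical ganciclovir, so these totals rest on an assumption.
- Topical 25%: 7.0 + 18.2 + 7.0 = 32.2
- Topical 65%: 7.0 + 18.2 + 18.2 = 43.4
- 60% in all three arms: 84 × 0.60 = 50.4

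With 35 per arm and no loss, the same scenarios run from 35 × (0.25 + 0.65 + 0.25) = 40.3 to 105 × 0.60 = 63.

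**Step 5. Share of on-study taps.** SAP Table 1 expects 105 participants to complete Trial I, hence about 105 day-7 taps.
- 32.2 / (105 + 32.2) = 23%
- 43.4 / (105 + 43.4) = 29%
- 50.4 / (105 + 50.4) = 32%

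**Step 6. Missed events.** This would need a complication rate and a time of onset. The documents give neither, so no expected number can be computed.

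**Step 7. Exit against continued visits.** The schema has the participant leave at recurrence. Section 7.2.4 has a participant with an SAE continue scheduled visits if possible. For a serious complication of paracentesis #3 both apply, and nothing says how they fit together.

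**The case against.** The strongest reply is that the reporting duty does not lapse. The 24-hour rule in 7.2.5 has no end date, 7.2.1 covers anyone who ever took study medication, the SAE list in 7.2.3 has categories that could include both harms, and 7.3.2 gives a further route for unanticipated problems, timed from the investigator's awareness. An injury evident during the tap can be entered the same day, because the adverse-event log is available at every exam. Participants come from the sites' own patient populations (5.3) and leave with active uveitis, so many may well be seen again. All of this stands. It rules out the reading, which the exit rule may suggest, that harms of this tap go unreported or that their rate is zero by construction. It also means that delayed onset is an inference, since the documents give no onset times. It does not supply a scheduled contact.

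A second reply is that for an extremely rare event, zero in some 50 taps is likely even with perfect follow-up. This also stands: with no events in 50 taps, the one-sided 95% upper bound is 1 − 0.05^(1/50) = 5.8%, so the trial could not estimate the rate closely. The reason for the change is to find the individual event and to apply the same ascertainment in both trials, not to gain precision.

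Third, 65% on oral is the detectable alternative in SAP 3.3, not a forecast. Protocol 8.2 gives a 36-point difference, hence 61%, or 28 × 0.61 = 17.1 oral taps. The difference is small beside the uncertainty about topical.

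Finally, post-tap instructions might be in the separate paracentesis consent forms (7.1.3) or the manual of procedures (11.3), which are not in the reviewed text. If so, the protocol need only point to them.

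**Conclusion.** The point holds as a gap in active ascertainment. In Trial II, at Exams 2 to 8 and at unscheduled flare visits, no scheduled safety contact or adverse-event window follows paracentesis #3, and a delayed harm would come to light only by spontaneous report. The same procedure in Trial I has a safety evaluation 14 days later.

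On the SAP's planning figures this concerns about 7 placebo and 18 oral participants. The total is about 32 to 50 once a topical risk is assumed, or 23-32% of on-study taps. The imbalance by arm exists only to the extent that recurrence differs by arm.

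A reader might go further and conclude that the trial cannot observe these complications at all, or that a known number will be missed. The documents support neither conclusion. Sections 7.2.4 and 1.1 do, however, conflict for a serious complication of this tap and must be reconciled.

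**What to change.** - In the Schema, the Schedule of Activities and 7.2.5, state that AE and SAE ascertainment stays open for a defined period after paracentesis #3 despite study exit, and that this applies to unscheduled flare visits as well. The existing coordinator can record it on the existing adverse-event form. The length of the period and the form of contact are for the investigators to set; the 14 days between Trial I Exams 2 and 3 is an internal reference point, though the documents do not say it was chosen as a post-tap safety window.
- Reconcile 7.2.4 with exit at recurrence in 1.1, so that the follow-up of a participant with a serious complication of the tap is unambiguous.
- In the SAP, tabulate procedure complications per paracentesis and separately from drug adverse events, with the number of taps by arm as denominator.

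The cost is protocol and SAP wording plus one brief contact or chart check for about 30-50 participants. No new procedure or staff is needed.

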1.2 Schedule of Activities (SOA)

Tasks/Forms	Trial I Visits				Trial II Visits		
	Exam #0	Enroll/ Randomize Exam #1	Exam #2	Exam #3	Enroll/ Re-Randomize Exam #1	Exam #2-7	Exam #8
Eligibility/ Screening Form		X			X		
Consent/HIPAA		X			X		
Baseline History Form		X					
Clinical Eye Exam Form		X	X	X	X	X	X
REDCap patient		X			X		
Treatment initiation		X			X		
Laboratory orders (CBC, Cr, pregnancy	X		X	X		X	X
SAE/side effect evaluation			X	X		X	X
Calendar/ medication log***			X	X		X	X
Patient Dropout		(x)	(x)	(x)		(x)	(x)
Protocol Deviation Form	(x)	(x)	(x)	(x)	(x)	(x)	(x)
Adverse Event Narrative/Log	(x)	(x)	(x)	(x)	(x)	(x)	(x)
AC paracentesis	X		X			(x)	(x)

Confocal microscopy				X			X
(x)-if applicable							

2 INTRODUCTION

2.1 Background

Immunocompetence does not protect one from cytomegalovirus (CMV) ocular inflammation (uveitis). While CMV retinitis causes blindness in patients with HIV/AIDS, recurrent and chronic inflammation anterior uveitis in immunocompetent individuals can also lead to blindness by causing glaucoma and corneal decompensation.

There is debate whether each case of active CMV anterior uveitis requires treatment.¹⁻² Nevertheless, treatment strategies include oral antiviral and topical antiviral therapy.³⁻⁵ There is relative equipoise as to whether oral or topical antiviral treatment and management of CMV anterior uveitis is most effective.⁶

Once CMV anterior uveitis is controlled long-term antiviral prophylaxis has been suggested to decrease recurrences, but is not uniformly used.⁷ There are no prospective randomized trials demonstrating whether long-term antiviral prophylaxis reduces recurrences and associated sequela of corneal decompensation or glaucoma.³⁻⁴

Clinical features of inflammation are the primary way that disease activity is assessed and monitored, but whether each recurrence is mediated by active viral replication and whether viral genome mutations and polymorphisms play a role in persistence and recurrence is largely unknown.

This proposal leverage's our team's expertise in metagenomic deep sequencing and the design and implementation of randomized controlled trials. We have led randomized placebo-controlled trials in infectious keratitis in the Steroids for Corneal Ulcers Trial (SCUT, U10 EY015114) and in non-infectious uveitis in the First-line Antimetabolites for Steroid-sparing Therapy (FAST, U10 EY021125) trial. Our group has significant prowess in identifying the entire genome of infectious pathogens as well as identifying mutations that confer resistance to medications.⁸⁻¹⁰ Additionally, our group has characterized host transcriptome features in a variety of inflammatory conditions.^{9,11} We also have substantial experience in conducting successful multicenter, international randomized trials. Including prior trials such as SCUT, FAST, the Mycotic Ulcer Treatment Trial (MUTT, U10 EY018573) and currently active trials like Azithromycin Reduction to Reaching Elimination of Trachoma (ARRET, UG1 EY030833), Adalimumab in JIA-associated Uveitis Stopping Trial (ADJUST, UG1 EY029658), and the Village-Integrated Eye Worker Trial (VIEW, UG1 EY028097).

There are no clear guidelines regarding the treatment for acute inflammation in CMV anterior uveitis and no guidelines regarding the most effective strategy for preventing recurrences of CMV anterior uveitis once clinical control is achieved. We seek to enroll participants with PCR-proven CMV anterior uveitis into a sequential double-masked placebo-controlled randomized clinical trial in the US and Asia.

2.2 Study Rationale and Significance

Cytomegalovirus made headlines in medicine and ophthalmology as a major cause of blindness during the HIV/AIDS epidemic. CMV retinitis causes a coagulative retinal necrosis of the peripheral and macular retina and can involve the optic nerve, all of which can lead to irreversible blindness. The risk factors for CMV retinitis are well known. Patients with CD4 counts lower than 50 cells/microliter have a 4-fold higher risk for developing CMV retinitis compared to those with CD4 counts greater than 100 cells/microliter. While the HIV/AIDS epidemic is over in developed countries, CMV retinitis is still encountered in patients with a variety of immunodeficient states or with advanced age.¹² The management for CMV retinitis is well developed. Systemic therapy consists of intravenous administration of antiviral medication that targets the viral kinases of CMV, which is necessary for its replication. Additionally, intraocular injection therapy using antivirals has been a standard approach, including, for a time, a ganciclovir-eluting implant. **There is, however, no defined therapeutic regimen for managing acutely active CMV anterior uveitis or whether long-term antiviral prophylaxis prevents recurrences.**

Antiviral resistance mutations play a role in CMV infection, particularly in HIV/AIDS and in organ transplant patients. The chronic exposure to prophylactic dosing of antiviral in an immunodeficient host plays a role in the development of CMV antiviral resistance.¹³ This has implications for the eye as up to nearly 30% of patients on long-term antiviral prophylaxis for a history of CMV retinitis are found to have CMV resistant to standard antiviral therapy, which is associated with more areas of retinitis and worse vision as well as putting the other eye at risk for the development of CMV retinitis.^{14,15} Additionally, plasma CMV viral loads > >400 copies/mL is associated with antiviral resistance due to mutations in the *UL97* and *UL54* genes.¹⁶ **Does long-term antiviral prophylaxis for CMV anterior uveitis also promote the development of antiviral resistance?**

A detectable CMV viral load in the blood predicts the development of CMV disease (including retinitis) as well as death with or without antiretroviral therapy. Plasma CMV loads >400 copies/mL is associated with an increased risk of CMV retinitis progression.¹⁶ Moreover, the viral load in the eye (as assessed from the aqueous or vitreous fluid in patients with CMV retinitis) is correlated with the area of retinitis involvement.¹⁷ **CMV viral load may be correlated with disease severity in CMV anterior uveitis.**

CMV anterior uveitis may be characterized by a self-limiting course even without therapy, by frequently recurrent disease, or chronic inflammation. Such a wide array of phenotypes has led to a lack of precise treatment protocols. **Whether treatment of CMV anterior uveitis acutely with antiviral medication results in a more significant reduction in viral load, which may be associated with improved outcomes** with respect to corneal endothelial cell count, intraocular pressure, incidence or progressive glaucoma, and, visual acuity is unknown.

Long-term antiviral prophylaxis can beget the development of antiviral resistant CMV – in immunodeficient patients. In patient with acquired immunodeficiencies, such as HIV/AIDS, or organ transplant patients iatrogenically immunosuppressed to prevent graft rejection, antiviral resistant CMV may develop. Antiviral resistant CMV can be found in 19.5% of patients with

HIV/AIDS and in 11.4% of organ transplant patients.¹³ Others have found that by 9 months of antiviral therapy, 27% of HIV/AIDS patients developed antiviral resistant CMV.¹⁸ Further studies have identified mutations or polymorphisms in the *UL97* gene from the blood and vitreous in HIV/AIDS patients.¹⁹ Thus, mutant CMV in the peripheral blood is reflected in the replicating virus in patients with antiviral resistant CMV retinitis.

Antiviral resistance is associated with progressive and new CMV ocular disease. In immunocompromised patients, the development of antiviral resistant CMV in their blood or urine portends poor clinical outcomes, including ocular disease as such patients develop progressive retinitis in those with prior CMV retinitis or development of retinitis in their previously affected contralateral eye.^{14,18,20} Antiviral resistance most commonly involves mutations in the genes encoding viral kinases (*UL97* and *UL54*). Indeed, mutations in these two viral kinase genes is associated with a greater increase in the area of retina involved with CMV retinitis as well as a 9-fold increased risk of having contralateral involvement with CMV retinitis.¹⁵ Whether recurrent CMV anterior uveitis is mediated by antiviral resistance is unknown. The present proposal will be able to identify such resistance.

